#### The Specific Aims of this study are:

Aim 1: Determine the efficacy of bupropion and fluoxetine in treatment of MDD in CKD patients.

**Aim 2**: Determine whether longitudinal change in MDD symptoms, cognitive dysfunction, and fatigue differ between bupropion and fluoxetine.

**Aim 3**: Determine whether longitudinal change in MDD symptoms, cognitive dysfunction, and fatigue correlate with change in inflammation, measures of TRP availability to brain, or neurotoxic TRP metabolites.

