# Data Analysis, Statistical Considerations, and Testing of Hypotheses:

Determination of Sample Size: Hypothesis 1 concerns within-treatment group improvement of

Version #: 17, IRB #203076

PI: [name]

depression. With four post-baseline measures, calculation of power requires an estimate of the matrix of correlations among the repeated measures. We specified a medium effect size averaged across the postbaseline measures (Cohen's d=0.5 SD, 1988), unadjusted alpha of 0.05. We specified compound symmetry among the measures with r=0.50 because the measurements are relatively close in time. With these specifications, it is possible to calculate the standard error of the difference between baseline and the average of the post-baseline measures. With N=20, IBM SamplePower3's (IBM SPSS, 2000) module for the t-test for paired observations indicates power=0.78 with N=20. We confirmed this result with a simulation with 1000 datasets with the structure described, performing mixed effects analyses as described below. The simulation yielded an empirical power estimate of 0.79 for Hypothesis 1. We also evaluated a banded covariance structure in which the correlations fell off from .50 to .32 over time, and found that yielded power=0.75. Hypothesis 2 concerns between group differences. Power was calculated using Hedeker's RMASS2 software for mixed models with longitudinal data. Specifications were as above but the effect size was adjusted for the use of a baseline covariate and the design involves two groups of N=20 each assessed at four occasions. In this case, power is 0.80 to detect a standardized mean difference (Cohen's d) of 0.6. This is slightly larger than the conventional medium effect size of d=0.50. The analyses for Hypothesis 3 involves using the TRP/LNAA ratio as a covariate in mixed effects regression models with the same design structure and analytic plan as the between-groups models for Hypothesis 2. Converting Cohen's d to the correlation coefficient equivalent, d=.6 is roughly equal to r=.30. Cohen's convention for a medium correlation. Evidence that these assumptions about effect sizes are probably quite conservative can be found in previously described effects of bupropion [68, 70, 90, 116-120] and fluoxetine [28, 60, 104, 116, 121] on symptoms of major depression, cognition, and inflammation.

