General Methods: Given that a primary goal of the current study is to obtain data to justify and support the feasibility of a future definitive trial, a variety of data necessary for this, including data on tolerability and safety (see below), will be obtained. For example, subject disposition will be summarized with a table indicating the number of subjects screened, the number of screen failures by reason, the number enrolled, the number who dropped out (by reason), and the number completing the study. Random double-blind assignment of patients to fluoxetine or bupropion is expected to yield similar distributions of measured and unmeasured variables of interest. This design provides a strong basis for making inferences about causal relationships between variables by controlling a priori for a wide range of patient and situational factors, thereby increasing the validity of estimates and inferential tests. In betweengroups analyses, variables that are related to outcome which differ between groups will be included as predictors in a logit model predicting group assignment, and the predicted values of this model will be incorporated as a covariate in all subsequent analyses. This includes factors that could influence treatment response [125-127], including number of prior episodes (>2 or not), treatment response vs. remission during treatment, and sex [128]. Continuously distributed outcomes will be summarized with the sample size, mean, standard deviation, median, minimum and maximum and categorical or binary outcomes with counts and percentages. Distributions will be examined to identify potentially influential observations (outliers) and suggest transforms (e.g., log) to normalize. The final report containing formatted tables and embedded graphics will be produced in Microsoft Word directly from the database using the SAS Output Delivery System. Analyses will use all subjects with usable data. All statistical testing will be two-sided with a significance level of 5%. The Holm-Bonferroni step down method will be applied as necessary to correct for multiple testing. SAS Version 9.2 for Windows (SAS Institute, Cary, North Carolina) will be used throughout.

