Tolerability and Safety: We will determine incidence rates for all adverse events and treatment emergent adverse events will be determined using the SAFTEE. Treatment emergent adverse events will be defined as those that were not present before the first administration of drug, but occurred after the first administration, or that were present before the first administration but increased in severity or frequency after the first administration. Incidence rates for all adverse event and treatment emergent adverse events will be compared between medication groups using chi-square for frequencies with any events or Poisson regression for counts of numbers of events adjusting for time at risk using log time as an offset variable. The numbers of subjects withdrawing from the study for each reason will also be compared across groups using survival analysis on time to study discontinuation.

Version #: 17, IRB #203076

PI: [name]

**Testing Hypothesis 1**. Both antidepressants will be efficacious based on change in Ham-D scores over time. The primary analyses will be mixed effects regression models with repeated measures (baseline, 1, 4, 8, 12 weeks) performed separately in the medication groups. The fixed effect is time, and the hypothesis test is an *a priori* contrast comparing the baseline value with the average of the four post-baseline values. In secondary analyses, patients will be categorized as responders and remitters, with response defined as a 50% or greater improvement in Ham-D score with total score ≤ 15 at the 12 weeks compared with baseline and remission [129] as having had a treatment response plus a final Ham-D score ≤7.

**Testing Hypothesis 2**. Changes in cognition, fatigue, and depression will be evaluated between and within treatment groups. Changes in BFI and cognition should be greater in bupropion SR-treated patients [30, 32, 89, 130-140]. These analyses will use mixed effects regression models with repeated measures. Treatment group, time and their interaction are the fixed independent variables. Change in Ham-D, BFI and cognitive dysfunction (3MS, MSIT, and n-back performance) are the time-varying dependent variables. All subscales of the BFI will be summarized by time point.

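### The propensity covariate may include response or remission status, a post-randomisation outcome, and can then bias the average between-drug effect on Ham-D

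*Combined protocol and SAP*

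**What the plan says.** The rule is in the General Methods paragraph of the section on data analysis and testing of hypotheses. For comparisons of the two arms it says that "variables that are related to outcome which differ between groups will be included as predictors in a logit model predicting group assignment". The fitted score is then carried forward, since it says that "the predicted values of this model will be incorporated as a covariate in all subsequent analyses". The paragraph goes on to name factors covered by this rule: "number of prior episodes (>2 or not), treatment response vs. remission during treatment, and sex". It sets no threshold for when a variable differs between groups. Nothing in the document confines these variables to measurements taken before randomisation.

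The only definitions of the two terms are under Testing Hypothesis 1. There is "response defined as a 50% or greater improvement in Ham-D score", together with a ceiling of 15 on the total score at 12 weeks. Remission is defined "as having had a treatment response plus a final Ham-D score" of 7 or less.

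Ham-D is also a between-drug outcome. Aim 2 is to "Determine whether longitudinal change in MDD symptoms, cognitive dysfunction, and fatigue differ between bupropion and fluoxetine", and under Testing Hypothesis 2 "Changes in cognition, fatigue, and depression will be evaluated between and within treatment groups". For that comparison, Determination of Sample Size states that "power is 0.80 to detect a standardized mean difference (Cohen's d) of 0.6".

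**The concern.** Sex and number of prior episodes are fixed before treatment starts. Response or remission under study treatment is partly caused by the drug and is computed from the Ham-D scores being compared. Adjusting the Ham-D comparison for it conditions on part of the effect being estimated.

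The entry rule does not protect against this. The status is related to the Ham-D outcome almost by construction, and it differs between arms most often when the drugs truly differ at week 12. The adjustment therefore tends to operate when there is an effect to find.

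The item also cannot be applied as written. Remission requires response, so a contrast of response with remission has no place for non-responders. A patient without a week-12 Ham-D has no defined status.

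At stake is the average between-drug Ham-D estimate from a pilot whose stated purpose includes supplying data for a definitive trial.

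**Working it through.** **1. The plan's own power figure (Hypothesis 2).** Inputs from Determination of Sample Size: 20 per arm, four occasions, compound symmetry with r = 0.50, d = 0.6, effect size adjusted for a baseline covariate. Two-sided alpha of 0.05 is from General Methods.

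- Variance of the mean of four measures: (1 + 3 × 0.50)/4 = 0.625, so SD = 0.791.
- Adjusted effect: 0.6/√(1 − 0.50²) = 0.693.
- Standardised effect: 0.693/0.791 = 0.876.
- Noncentrality: 0.876 × √(20/2) = 2.77.
- Power, normal approximation: Φ(2.77 − 1.96) = 0.79, against the stated 0.80.

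The stated figure reproduces. It allows for a baseline covariate only. A full ANCOVA variance, 0.625 − 0.50² = 0.375, would give 0.873, so an ANCOVA simulation should show more power than 0.80 before any problem arises.

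**2. Why the covariate acts like the outcome.** If a binary status is the only predictor in the logit model, the fitted probability takes two values, one per status. Using it as a covariate is then the same as adjusting for the status itself.

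**3. Simulation.** From the document: 20 per arm, r = 0.50, the response definition, both halves of the entry rule. Assumed, not in the document: baseline Ham-D 24, SD 5, common fall 10 points, true average effect 0.60 SD, entry when both halves are met at p<0.05, responder coding (yes/no), complete data. The model is ANCOVA of the post-baseline mean on group, baseline and propensity value. Ranges come from repeated independent runs.

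| Drug effect over time (true average 0.60 SD) | Estimate under the entry rule | Estimate if status always enters |
|---|---|---|
| Constant from week 1 | 0.46–0.49 | 0.41 |
| Growing to week 12 | 0.28–0.30 | 0.24–0.27 |
| Early, gone by week 12 | 0.59 | – |
| Crossing by week 12 | 0.62 | 0.71 |

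For the constant effect, power is about 0.70. The same ANCOVA with baseline variables only gives an estimate of 0.60 and power of about 0.85. The retained share is 0.46/0.60 = 77% to 0.49/0.60 = 82%. For the growing effect it is about 0.3/0.6, or half. With no true Ham-D difference the estimate is 0.00.

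Other codings under a constant effect (same Ham-D values, entry at p<0.05 or p<0.10) give 0.46–0.50 for three levels (neither, response, remission) and 0.54–0.57 for remission yes/no. Under responder coding, the status entered in 26–51% of trials across the settings tried, which also included SD 6 with fall 11.

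**4. Bias or small-sample noise?** At 1000 per arm with the status always included, the adjusted effect was still 62% (three levels) and 77% (remission) of the unadjusted one. It is bias.

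**5. Mixed model with group, time and interaction.** In 149 simulated datasets (SD 6, three-level status always included), the average group effect moved from −3.71 to −2.76 points. The group-by-time terms did not change, as expected for a time-constant covariate in complete data.

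**6. Fatigue.** With a Ham-D effect of 0.60 SD and an assumed Ham-D/BFI correlation of 0.5 or 0.6, a true BFI effect of 0.60 was estimated at 0.53–0.59, and a true zero shifted by 0.01–0.05. If one score, entered on arm difference alone, is carried into all models, the figures are 0.52–0.59 and 0.01–0.08, and a true BFI null is rejected at 0.04–0.06. Cognition was not computed.

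**The case against.** **Earlier treatment was meant.** The factors are introduced as possible influences on treatment response, and the baseline ATRQ records earlier antidepressant response. This may be the intent. But the text refers to treatment in progress, does not mention earlier courses, and defines the two terms only from study Ham-D. If earlier treatment was meant, the sentence still needs correcting.

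**Entry is conditional.** True, and the main figures in the working apply the entry rule. The condition lowers the size of the bias but does not remove it.

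**The test may be the interaction.** Aim 2 concerns longitudinal change and the Hypothesis 2 model includes group by time. If that term alone is tested, complete-data inference is unaffected. The document does not settle this: the power statement concerns a standardised mean difference with a baseline covariate, which points to an average effect.

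**The predicted scenario is mostly unaffected.** The plan expects both drugs to work on depression and bupropion to do better on fatigue and cognition. If the drugs do not differ on Ham-D, the Ham-D estimate is not biased, and the fatigue shifts found are small. This limits the severity. Aim 2 still asks the Ham-D question.

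**Stronger readings a reader might infer.**
- That the bias is always toward zero. It is not: see the early-only and crossing profiles.
- That forcing the status in under a constant effect (0.37–0.51 across codings and settings) is the worst case. It is not: a growing effect gives 0.24–0.27.
- That power falls from the plan's 0.80. The valid comparator is about 0.85, from the same ANCOVA.
- That cognition results are shown to be biased. Any shift depends on their correlation with Ham-D, for which the document gives no figure.

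**Conclusion.** The concern holds in a bounded form. As written, the plan lets a post-randomisation outcome into the covariate used for between-drug analyses, and that outcome is derived from the Ham-D scores being compared. If it enters, the average Ham-D effect is biased. In the ordinary case, where the week-12 and average differences share a sign, the bias is toward zero: roughly a fifth of a constant 0.60 SD effect is lost under responder coding, and about half of one that grows to week 12.

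These sizes rest on assumed Ham-D means, SD, entry threshold and coding, and dropout was not simulated. The existence of the bias follows from the text; its size and direction depend on those assumptions and on the effect's course over time.

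Not affected: the within-drug Hypothesis 1 models, the group-by-time terms in complete data, and Ham-D estimates when the drugs do not differ on Ham-D. This should be fixed before analysis; it does not undermine the trial's design.

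**What to change.** In General Methods, delete the middle item of the list "number of prior episodes (>2 or not), treatment response vs. remission during treatment, and sex". Add that, in all between-drug comparisons, only variables measured before randomisation may enter the propensity model or serve as adjustment covariates. This includes pain: the Research Plan intends to control for chronic pain, which is measured repeatedly, so only its baseline value should be used if it is adjusted for.

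State that the restriction does not apply to the Hypothesis 3 predictors (TRP/LNAA ratio, CRP, quinolinic acid) or to the time-at-risk offset in the adverse-event models.

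If response to earlier antidepressant treatment was intended, say so and take it from the baseline ATRQ.

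The cost is a wording change to the analysis section, with no new data, visits or patients.

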#### 1. Purpose and Objectives

The proposed study will evaluate the response and remission rates for major depressive disorder (MDD) in chronic kidney disease (CKD) patients treated with bupropion or fluoxetine for 12 weeks. In addition, the study will document the relative tolerability and safety, and longitudinally contrast the effects of bupropion and fluoxetine on measures of cognitive function, fatigue, inflammation, and tryptophan (TRP) and TRP catabolites in blood. It is hypothesized that both drugs will significantly reduce MDD symptoms from baseline, and be tolerable and safe, but bupropion will be associated with greater reduction in proinflammatory cytokines, cognitive impairment, and fatigue compared with fluoxetine.

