# 3. Study Design

The current study proposes to randomly assign 40 CKD patients with MDD to 12 weeks of open label, flexible dose treatment with either bupropion (N=20) or fluoxetine (N=20).

[NOTE: We are requesting to enroll up to 50 subjects/with 40 completers. One of the outcome measures will be the number of weeks of treatment that a person completes. This is a preliminary feasibility and pilot study, so establishing an estimate of drop out rate will be important for when we design the "definitive" study in the future.]

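### The hypothesis that each drug is tolerable and safe has no per-drug inference: every planned safety test compares one active drug with the other, and no confidence intervals are specified

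*Combined protocol and SAP*

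**What the plan says.** All references are to the combined protocol and SAP.

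- **Section 1, Purpose and Objectives**, makes two safety statements. One is comparative: "the study will document the relative tolerability and safety". The other concerns each drug: "It is hypothesized that both drugs will significantly reduce MDD symptoms from baseline, and be tolerable and safe".
- **Data Analysis, Tolerability and Safety paragraph.** Incidence of adverse events and of treatment-emergent events is determined with the SAFTEE. Then: "Incidence rates for all adverse event and treatment emergent adverse events will be compared between medication groups using chi-square for frequencies with any events". Event counts go to Poisson regression with a log-time offset, and withdrawals are compared between groups by survival analysis of time to discontinuation.
- **Data Analysis, General Methods paragraph.** Binary outcomes are summarised as counts and percentages. A disposition table gives dropouts by reason. On testing: "All statistical testing will be two-sided with a significance level of 5" per cent, and "The Holm-Bonferroni step down method will be applied as necessary to correct for multiple testing".
- **Section 3, Study Design.** There are 20 patients per arm, in a study labelled a feasibility pilot: "We are requesting to enroll up to 50 subjects/with 40 completers".

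The plan gives no acceptability limit, margin, reference rate, confidence interval, power or precision figure for any group-level safety rate.

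**The concern.** The per-drug statement and the tests answer different questions. The tests' null hypothesis is that bupropion and fluoxetine have the same rate. That can be true when both are well tolerated and equally when both are poorly tolerated. With no placebo arm, reference rate or interval, nothing inferential in the plan speaks to either drug alone.

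Efficacy, the other half of the same sentence, is handled differently. Hypothesis 1 is tested within each medication group, so the plan already provides per-drug inference for depression but not for tolerability.

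General Methods says that the tolerability and safety data are meant to help justify a later definitive trial. Whoever designs that trial needs each drug's rate and its uncertainty. Percentages from about 20 patients beside a between-drug p-value do not show that uncertainty.

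**Working it through.** **1. The plan's own figures.** Power is stated only for efficacy and the other numbered hypotheses. For Hypothesis 1 (n = 20, d = 0.5, r = 0.50, four post-baseline measures), the variance of the contrast is (1 + 3 × 0.5)/4 + 1 − 2 × 0.5 = 0.625. The noncentrality is 0.5/√(0.625/20) = 2.83 and the paired-t power is 0.765, against a stated 0.78. For Hypothesis 2, d = 0.6/√(1 − 0.5²) with the same averaging gives 0.79 against a stated 0.80. Both agree within 2 points. There is no safety figure to reproduce.

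**2. Inputs for the safety tests.** The documents supply 20 per arm, up to 50 enrolled (50/2 = 25 per arm), two-sided 5%, and the chi-square test. The event rates are assumptions, shown as a range, because the risk tables give only broad frequency bands.

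**3. Per-drug claim.** For all pairs of binomial counts (i, j), sum P(i)P(j) over pairs where the uncorrected Pearson chi-square has p ≤ 0.05. With a true 40% rate on both drugs and 20 per arm, the test rejects with probability 0.048, so it is non-significant in 1 − 0.048 = 95% of trials. A larger sample does not help: under equal rates a 5% test stays non-significant about 95% of the time, however high the common rate.

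**4. Relative claim.** The same enumeration gives the following power, with the miss probability (1 − power) in brackets:

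| Assumed rates | 20 per arm | 25 per arm |
|---|---|---|
| 10% vs 20% | 0.14 (0.86) | 0.17 (0.83) |
| 10% vs 30% | 0.36 (0.64) | 0.45 (0.55) |
| 20% vs 40% | 0.29 (0.71) | 0.35 (0.65) |
| 20% vs 50% | 0.53 (0.47) | 0.64 (0.36) |
| 10% vs 50% | 0.84 (0.16) | 0.91 (0.09) |

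The chi-square is weak for moderate differences and adequate for very large ones.

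**5. The other two analyses.** For Poisson counts, SE(log rate ratio) = √(φ[1/(n·r) + 1/(n·r·RR)]), where r is events per patient in the lower arm and φ is the dispersion. With n = 20, r = 3 and RR = 2, power is 0.99, 0.87 and 0.72 at φ = 1, 2 and 3. With r = 3 and RR = 1.5 it is 0.68, 0.41 and 0.29. With r = 1 and RR = 2 it is 0.72, 0.43 and 0.31. Counts of frequent events can therefore show a doubling.

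For discontinuation at 25 per arm, 10% vs 30%, the hazard ratio is ln 0.7/ln 0.9 = 3.39 with 25 × (0.1 + 0.3) = 10 events. Then √10 × ln 3.39/2 = 1.93, and power is Φ(1.93 − 1.96) ≈ 0.49.

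**6. What estimation would show.** The exact (Clopper-Pearson) upper 95% limit for zero events is 1 − 0.025^(1/n): 16.8% for n = 20 and 13.7% for n = 25. Two events in 20 give 1.2% to 31.7%; five in 20 give 8.7% to 49.1%. As a between-drug example, 6/20 vs 2/20 gives chi-square = 40 × (6×18 − 2×14)²/(20×20×8×32) = 2.5, p = 0.11. The Newcombe 95% interval for the difference is −5 to +43 points. The p-value alone hides that range.

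**The case against.** The strongest reply is that the error is not in the text. Safety is absent from the three Specific Aims, the three numbered hypotheses and the sample-size paragraph. Relative tolerability is a stated objective, and a between-drug comparison is the natural analysis for it. The plan also has descriptive content: SAFTEE incidence, dropouts by reason, weeks of treatment completed as an outcome, and a per-patient QTc check. Low power for harms is unavoidable in a pilot of this size.

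Most of this stands, and it rules out several stronger readings that a reader might infer:

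- *That the plan will treat p > 0.05 as proof of safety.* It nowhere says so.
- *That significance tests are the only safety output.* Incidence and disposition are reported too. They lack an interval or a group-level limit.
- *That a null result is nearly assured.* This fits equal rates, small differences and rare events. It does not fit 10% vs 50%, or frequent event counts with a rate ratio of 2.
- *That Holm will suppress harm signals.* The 5% level is set for all testing, but Holm is a separate sentence and applies only as necessary. No family of adverse-event tests is defined, so no Holm penalty can be calculated from the documents.

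The reply does not cover the per-drug hypothesis. It is written in the purpose section, and no planned interval or test addresses it. Pilot status favours estimates with stated precision over tests.

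**Conclusion.** The point holds as a mismatch between a stated per-drug hypothesis and analyses that are inferential only between drugs. That part needs no assumed event rate beyond the 40% illustration, and no sample size cures it. The secondary part, weak power for the relative comparison, depends on assumed rates: at 20 to 25 per arm the chi-square misses a 20-point difference such as 10% vs 30% or 20% vs 40% with probability 0.55 to 0.71. It does not extend to very large differences or to frequent event counts. The consequence is limited to how safety is reported and carried into the next trial; the efficacy analyses are unaffected. The change is worth making because it is nearly free.

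**What to change.** **Tolerability and Safety paragraph**
- For each drug, report the proportion with adverse events, with treatment-emergent events and with withdrawal for adverse events, each with an exact 95% confidence interval. Base statements about a drug's tolerability on those intervals.
- For the comparison, report the risk difference (for example with a Newcombe interval) or the rate ratio with a 95% interval, alongside or in place of the p-value.
- State that a non-significant difference between the drugs is not evidence of safety or of similar tolerability.

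**Section 1**
- Replace the per-drug safety hypothesis with the aim of estimating each drug's tolerability, and state the attainable precision: no events in 20 patients still allows a true rate up to 16.8%, and in 25 patients up to 13.7%.

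**Cost.** Wording in two places and a few extra table columns, with no added patients, visits or data. The safety conclusion becomes more modest.

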Participants will receive the study medication during the baseline assessment and instructed to begin the medication on day 1 (1st dialysis day) of week 1 of the study. For patient on hemodialysis or peritoneal dialysis, generic bupropion SR will be dosed at 150 mg on the 1st and the 3rd dialysis day of each week with doses adjusted upward or downward based on tolerability. The initial dose of bupropion-SR is based on the findings of Worrall et al [80], who measured plasma bupropion levels in a pharmacokinetic study of bupropion in HD patients. For patient not on hemodialysis or peritoneal dialysis, generic bupropion SR tablet will be dosed at 150 mg daily. Bupropion SR doses will be adjusted upward or downward based on tolerability and response. Fluoxetine will be started at 10 mg/day for the first week and then increased, as tolerated to 20 mg/day for weeks 2–4. After this, doses will be adjusted based on clinical response and side effects up to a maximum dose of 60 mg/daily by week 10 [62]. At the week 12 visit, the participants will stop the medication or may undergo a 1-2 week taper (depending on maintenance dose) if they are on a dose of fluoxetine that is higher than 20 mg.

Subjects will be seen during weeks 1, 2, 3, 4, 6, 8, 10, and 12 in face-to-face meetings by a rater blind to study medication and a study physician for Ham-D ratings, CGI, medication accountability, and measurement of adverse events. On weeks 5, 7, 9 and 11, subjects will come in to return the previous week's pill bottles and pick up the current week's medication. Table 1 shows study procedures. Medication will be prepared by UAMS Research Pharmacy, labeled with the directions for use and contact information, and given to participants by study staff on a weekly basis. Compliance will be monitored using the MAFV at each scheduled encounter and by analysis of antidepressant blood levels. Results of a second EKG done during week 4 will be reviewed to ensure QTc interval is less than 500 msec.

In order to control for the potential confound of chronic pain we will characterize it with the physical and psychological pain scale and with two objective measures, i.e. the pressure pain threshold and the Quantitative Sensory Test (QST).

Version #: 17, IRB #203076

PI: [name]

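### The primary Ham-D model for Hypothesis 1 leaves out the blinded scores at weeks 2, 3, 6 and 10, so it can slightly overstate improvement if patients leave after a poor score

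*Combined protocol and SAP*

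**What the plan says.** Section 6 (Research Plan) of the combined protocol and SAP sets the visits: "Subjects will be seen during weeks 1, 2, 3, 4, 6, 8, 10, and 12 in face-to-face meetings". Ham-D is rated at each of them by a rater blind to medication, and Table 1 marks it at baseline and at all eight post-baseline visits.

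Under Testing Hypothesis 1, the primary analysis is "mixed effects regression models with repeated measures (baseline, 1, 4, 8, 12 weeks) performed separately in the medication groups". The test is an a priori contrast "comparing the baseline value with the average of the four post-baseline values". The sample-size paragraph rests on the same structure: "With four post-baseline measures, calculation of power requires an estimate of the matrix of correlations among the repeated measures".

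The General Methods paragraph promises to analyse every subject with usable data. That rule is about subjects, not visits. Nothing explains the omission of weeks 2, 3, 6 and 10, and no supporting analysis brings them in.

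**The concern.** A likelihood-based mixed model gives valid estimates with dropout if, given the data in the model, dropout does not depend on the unseen scores. A patient can leave early after any of seven visits (weeks 1, 2, 3, 4, 6, 8, 10), and four of these (2, 3, 6, 10) are invisible to the model. If a poor score at one of them prompts withdrawal, the missing-at-random condition could hold in the collected data and still fail in the analysed subset.

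The section on concomitant clinical management and study termination lists clinical worsening among the reasons for discontinuation, so the mechanism is plausible here. Patients who are doing badly would leave, and their earlier poor scores would not inform the later means. The estimate would then lean towards improvement. Hypothesis 1 is tested within each arm, so a bias common to both arms does not cancel.

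**Working it through.** **Inputs from the plan** (Determination of Sample Size; General Methods): N = 20 per arm; effect d = 0.5 SD averaged over the post-baseline measures; "We specified compound symmetry among the measures with r=0.50"; two-sided alpha 0.05, unadjusted; four post-baseline measures; stated power 0.78 (paired t module) and 0.79 (the plan's simulation).

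**Step 1: reproduce the plan's figure.** With k post-baseline scores under compound symmetry, in SD units,

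Var(mean of k scores − baseline) = 1 + (1 + (k−1)r)/k − 2r.

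For k = 4, r = 0.5: 1 + 2.5/4 − 1 = 0.625, so SD = 0.791 and SE = 0.791/√20 = 0.177. The noncentrality is 0.5/0.177 = 2.83. Power is 0.765 with 19 df and 0.797 with 76 df (mixed model). Both are within two points of the stated values.

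**Step 2: precision from the omitted visits.** With complete data and the contrast kept on weeks 1, 4, 8 and 12, adding visits does not change the SE. Under simulated dropout the SE fell by about 1% or less (for example 0.1911 to 0.1889).

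**Step 3: bias under dropout.** Assumptions, none of them from the documents: 20% or 40% loss; chance of leaving depends on the last observed score, more weakly or more strongly; nobody leaves before week 1; true mean change 0.5 SD over weeks 1, 4, 8 and 12; covariance known; 2,000 simulated arms of 20 per scenario; Monte Carlo error 0.003 to 0.005 SD. Both models estimate the same contrast. Entries are bias in SD for weaker / stronger dependence; negative means improvement is overstated.

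| Correlation | Loss | Four visits | Eight visits |
|---|---|---|---|
| Compound symmetry, 0.50 | 20% | −0.011 / −0.014 | 0.000 / +0.004 |
| | 40% | −0.017 / −0.034 | +0.006 / 0.000 |
| Declining from 0.50 to 0.32 | 20% | −0.008 / −0.033 | +0.004 / −0.013 |
| | 40% | −0.025 / −0.037 | 0.000 / +0.002 |
| Exponential decay, 0.95 per week, plus noise | 20% | −0.011 / −0.020 | 0.000 / −0.004 |
| | 40% | −0.025 / −0.037 | −0.003 / −0.003 |

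Between 46% and 55% of simulated dropouts had their last score at an omitted visit. A separate run under compound symmetry gave four-visit biases of −0.023 at 20% loss and −0.026 at 30%.

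**Step 4: covariance estimated by REML.** With 22% to 23% loss driven by the latest score, the four-visit bias was −0.013 to −0.025 SD. The eight-visit bias was about −0.006 to +0.005 SD when the fitted structure suited the data. When compound symmetry was fitted to decaying correlations, the eight-visit model did worse than the four-visit model: +0.014 against −0.002 SD.

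**Step 5: scale.** For 20% to 30% loss the range is roughly 0.01 to 0.03 SD. Most results lie at or below 0.025 SD: 0.01/0.5 = 2% to 0.025/0.5 = 5% of the planned effect. Against the SE, 0.02/0.177 = 0.11 and 0.025/0.177 = 0.14, so about one-eighth. The top of the range is 0.03/0.177 = 0.17.

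**The case against.** The strongest reply is that the effect is too small to matter. In 3,000 further runs per scenario (nominal 20% to 30% loss, wholly score-driven), confidence-interval coverage was 94% to 95% for both models and root mean squared error differed by about 1%. The plan also lists reasons for leaving that need not follow a poor score: unspecified request or failure to return, adverse events and protocol violations. If only a quarter of the dropout hazard is score-driven (an assumption), the four-visit bias shrinks to between −0.003 and −0.008 SD, close to simulation error. This stands, and it limits the point to a refinement.

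The four-visit structure is also prespecified and matches the power calculation and the supplemental Hypothesis 3 models. A reader might infer a contradiction between schedule and analysis. There is none: collecting more visits than the primary model uses is consistent, only not explained.

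A nine-occasion unstructured covariance has 9 × 10/2 = 45 parameters, too many to estimate well from 20 patients. A structure must be imposed, and Step 4 shows that a poor choice can introduce a bias of similar size. This also stands, and it shapes the fix.

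What remains is that recorded, blinded primary-outcome scores are left out without a reason, in a pilot that lists clinical worsening as a reason for leaving, and that including them costs only wording.

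**Conclusion.** The point holds as a minor improvement. If dropout follows a recent poor score, the four-visit model overstates within-arm Ham-D improvement by roughly 0.01 to 0.03 SD at 20% to 30% loss, typically no more than about one-eighth of an SE. It would rarely change the Hypothesis 1 conclusion. The size rests on the assumed dropout pattern. The documents give an enrolment margin (up to 50 enrolled for 40 completers) and treat the dropout rate as something the pilot will estimate.

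Three stronger readings are not supported:

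- **That the plan gives up useful power.** Averaging all eight visits would cut the variance from 0.625 to 0.5625 and raise power from 0.77 to 0.81 (19 df). But that is a different estimand: the average timing moves from (1+4+8+12)/4 = week 6.25 to (1+2+3+4+6+8+10+12)/8 = week 5.75. It is not proposed here. With the planned contrast the gain is about 1%.
- **That using all visits removes dropout bias.** It reduces bias only where dropout depends on recorded scores and the covariance model is adequate. A patient who worsens between visits and never returns is missing not at random under either model.
- **That Hypothesis 2 also discards Ham-D or fatigue visits.** The Hypothesis 2 paragraph names no visits; four occasions appear only in its power calculation.

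**What to change.** In Testing Hypothesis 1, specify that each arm's model is fitted to baseline and all eight post-baseline Ham-D visits (weeks 1, 2, 3, 4, 6, 8, 10 and 12), with time as a categorical effect. Keep the a priori contrast of baseline against the mean of weeks 1, 4, 8 and 12, so that the question and the power basis do not change.

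Prespecify a structured covariance that lets correlation decay with time, for example a random intercept plus a spatial exponential term in weeks. Do not use plain compound symmetry as the working structure. If the four-visit model is kept as primary, give the reason and add the all-visit fit as a sensitivity analysis.

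The cost is SAP wording. No visit, assessment or patient is added. The one real downside is reliance on a structured covariance with 20 patients per arm.
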